4.9.2. Other Secondary Efficacy Endpoints Analyses

The secondary objective of this study is to test the hypothesis that LY3372689 slows cognitive and functional decline as measured by the secondary efficacy endpoint compared with placebo at end time point (76-124 weeks) in full study population and moderate tau sub population with early symptomatic AD. The main analytical approach to secondary efficacy endpoints is NCS2 as described in Section 4.8.2.1. The secondary object and the analysis method applies to all secondary efficacy endpoints including CDR-SB, ADAS-Cog₁₃, ADCS-iADL, and MMSE. The treatment effect based on data up to WK76 and based on data up to WK88 will be provided,

respectively. For the latter, the ‘overall’ treatment effect averaging across Week 64, Week 76, and Week 88 will be calculated.

The secondary efficacy endpoints will also be analyzed by Bayesian DPM (Section 4.8.1) in both moderate tau subpopulation and the full study population, respectively. The MMRM (Section 4.8.2.2) and time-PMRM (Section 4.8.3.2) analyses may be conducted as supplementary analysis.

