6.3. Measures to Minimize Bias: Randomization and Blinding

This is a double-blind study (study periods 2a and 2b), with design to maintain blinding to treatment. To preserve the blinding of the study, a minimal number of Lilly personnel will see the randomization table and treatment assignments before the study is complete.

For between-group comparability, participant randomization will be stratified by the investigative site, tau burden (moderate versus high) as defined by flortaucipir PET, and by prior or current use of any approved disease-modifying therapy for AD. Enrollment of high tau burden participants will be capitated at a predetermined proportion of the total enrolled population. Hence, study eligibility based on flortaucipir PET scan results may change as the study progresses. Assignment to treatment groups will be determined using an interactive web response system (IWRS). The IWRS will be programmed using the dynamic allocation (minimization) method of Pocock and Simon (1975), to balance the treatment arms using three factors: investigative site, tau burden, and prior or current use of any approved disease-modifying therapy for AD. This is to achieve balanced participant assignment between treatment arms as much as possible within each stratum and at the study level. Randomization into 1 stratum may be discontinued at the discretion of the sponsor.

Blinded site personnel will dispense study intervention and confirm that they have located the correct packages by entering a confirmation number found on the label into the IWRS.

The independent external DMC is unblinded to randomization.

If an investigator, site personnel performing assessments, or participant is unblinded, the participant must be discontinued from the study. In cases where there are ethical reasons to have the participant remain in the study, the investigator must obtain specific approval from a Lilly-designated Medical Monitor for the participant to continue in the study.

In case of an emergency, the investigator has the sole responsibility for determining if unblinding of a participant's treatment assignment is warranted for medical management of the event. The participant's safety must always be the first consideration in making such a determination. If a participant's treatment assignment is unblinded, Lilly must be notified immediately. If the

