where Y_{ij} denotes the clinical outcome at visit j for participant i , clinical outcome scores at baseline (prior to treatment) is Y_{i0} . T_i denotes the treatment arm for participant i . The parameter γ_i ($i=1, 2, \dots, k$) represents the subject-specific random effect for participant i . e^{θ_T} is the disease progression ratio (DPR) for treatment T and $e^{\theta_T} = 1$ for placebo; e^{θ_1} and e^{θ_2} represent the DPR of the low dose and the high dose, respectively. The parameter α_v is the mean change of placebo response from visit $v-1$ to v . ε_{ij} is the error term. Any stratification variables used for randomization such as investigator site and prior or current use of any approved disease-modifying therapy for AD will be included in the model. Baseline score, baseline age, concomitant acetylcholinesterase inhibitor (AChEI)/memantine use (yes/no) will be included in the model as well. Diffuse priors will be used for the Bayesian inferences in the DPM analysis. A DPR less than 1 corresponds to a slowing of disease progression; similarly, a DPR greater than 1 reflects some evidence of cognitive worsening. The DPM will be fitted to the data and Bayesian inferences will be summarized including posterior distribution of DPR and posterior probabilities of various DPR thresholds of interest (e.g., 0.75 which translates to 25% slowing of disease progression with LY3372689 group versus placebo). The null hypothesis is that the DPR between the LY3372689 group versus placebo equals 1.

The primary endpoint will also be assessed using natural cubic spline model with degrees of freedom 2 (NCS2) and MMRM to serve as sensitivity analyses. Additional models/analyses may be considered if deemed appropriate. The SAP will describe the planned analyses in greater details.

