1.3. Method of Assignment to Treatment

This is a double-blind study, with design to maintain blinding to treatment. To preserve the blinding of the study, a minimal number of Lilly personnel will see the randomization table and treatment assignments before the study is complete.

Participants who meet all criteria for enrolment will be assigned a study (patient) number at Visit 601 or Visit 1 and randomized to double-blind treatment at Visit 2. Participants will be randomized to LY3372689 or Placebo in a 1:1:1 ratio. For between-group comparability, patient randomization will be stratified by investigative site and tau burden (moderate versus high), and by prior or current use of any approved disease-modifying therapy for AD.

Assignment to treatment groups will be determined by a computer-generated random sequence using an interactive web response system (IWRS). Randomization into one stratum may be discontinued at the discretion of the sponsor. LY3372689 will be made available in blister packaging and will be given by a blinded nurse or other qualified blinded personnel, as described in the pharmacy manual. Site personnel will confirm that they have located the correct packages by entering a confirmation number found on the label into the IWRS.

For the first approximately 30 participants, the IWRS will be programmed to guarantee balance between the arms for the first interim analysis for safety; this is referred to as the burn-in period. After the burn-in period, participant randomization will then follow the dynamic allocation (minimization) method of Pocock and Simon (1975) to balance the treatment arms using investigative site as a factor. This is to ensure balanced participant assignment between treatment arms within each site at the end of the study.

2. Statistical Hypotheses

The primary efficacy analysis will be a Bayesian DPM conducted on the primary outcome iADRS. The primary efficacy analysis population will be those with moderate levels of tau pathology at baseline. A critical success factor (CSF) will be established of the following form:

- Probability (at least 25 % slowing of disease progression with LY3372689 relative to placebo) > 0.6 .

The Bayesian DPM will be utilized to calculate the posterior probability of at least 25% slowing. If the posterior probability exceeds the probability threshold for at least one LY3372689 versus placebo comparison, the trial will have been considered to have met its primary endpoint.

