4.8.2.1. Natural Cubic Spline (NCS) Analysis

A NCS model with 2 degrees of freedom (NCS2) (Donohue et al. 2023) will be used to estimate the difference in the change in iADRS score between the treatment arms. The NCS2 model has 3 knots over the observation time will be placed: 2 at the boundaries (minimum and maximum observation time), and 1 internal knot at the median observation time. The baseline estimates are restricted to be the same for all treatment arms. The model will be estimated using restricted maximum likelihood method (RMLE).

The iADRS score at baseline and at each of the scheduled post-baseline visits (according to SoA) will be included in model as a dependent variable. The analysis model will include the fixed effects of NCS basis expansion terms (two terms), NCS basis expansion term-by-treatment interaction (two terms), age at baseline, AChEI/memantine use at baseline (yes/no), and investigator site (pooled). Visit will be treated as a continuous variable with values equal to weeks between baseline and post-baseline exam dates, and the NCS basis function will be derived using these visits in weeks. An unstructured variance-covariance structure matrix will be used to model within-subject variance-covariance of residual errors across visits where visits are modeled as a categorical variable. If the unstructured variance-covariance structure matrix results in a lack of convergence, the following structures will be used in sequence:

- Heterogeneous Toeplitz covariance structure
- Heterogeneous autoregressive order 1 covariance structure
- Heterogeneous compound symmetry covariance structure, and
- Compound symmetry covariance structure

Mean change from baseline values, and the comparisons between change from baseline values by treatment arms will be estimated through the proper contrast set up. The Kenward-Roger approximation will be used to estimate the denominator degrees of freedom.

Percent slowing comparing to placebo group will be calculated as the least-squares (LS) estimates of differences in change from baseline between treatment groups, then divided by the LS estimates of mean change from baseline value from placebo group. A 95% CI for this percent slowing is calculated based on a Delta method (Beyene et al. 2005).

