4.9.1. Key Secondary Efficacy Endpoint Analysis

The key secondary objective of this study is to test the hypothesis that LY3372689 slows cognitive and functional decline in early symptomatic AD participants with elevated cortical tau burden as measured by iADRS compared with placebo through end time point (76 -124 weeks). The model setup will be the same as described in Section 4.8.1 and Section 4.8.2, with the inclusion of the tau burden (moderate versus high) as defined by flortaucipir PET in the model as a baseline covariate. The time-PMRM (Section 4.8.3.2) analysis may be conducted to assess the treatment effect from time-saving perspective.

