4.9.3. Other Secondary Endpoints Analyses

4.9.3.1. Analysis of Volumetric MRI

Analyses of the following volumetric MRI (vMRI) parameters will be conducted (right + left for all but whole brain volume and ventricular volume):

- Hippocampal volume (mm³)
- Atrophy of total whole brain volume (cm³)
- Enlargement of Ventricular volume (cm³)

To evaluate the changes in vMRI parameters, an MMRM model will be used to compare change from baseline to Week 76 between the treatment arms in the Efficacy Evaluable analysis set within moderate tau population and full study population, respectively.

The change from baseline at each post-baseline visit up to Week 76 will be the dependent variable. The model will include the fixed effects of treatment, visit as a categorical variable, treatment-by-visit interaction, and adjusted for baseline vMRI value and age at baseline. Baseline tau PET category will also be included as a fixed effect to the model when analyzing full study population. The null hypothesis is that the difference in LS mean between both the active treatment arm and placebo equal zero. Analyses including post-Week 76 visits may be included for exploratory purpose.

To assess the relationship of vMRI with efficacy endpoints up to Week 76, Spearman's rank correlation coefficient may be obtained on baseline and change from baseline on vMRI parameters versus change from baseline for iADRS, CDSR-SB, ADAS-Cog13, ADCS-ADL, and MMSE. This will be performed using participants who have both the clinical outcome and vMRI result at Week 52 and Week 76, respectively. This analysis may be performed in moderate tau subpopulation and/or the full study population. The correlation analysis including post-Week 76 timepoints such as Week 100 and Week 124 may be conducted for exploratory purpose.

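### The full-population NCS2 model for CDR-SB, ADAS-Cog13, ADCS-iADL and MMSE leaves out tau burden, a randomisation factor, and loses some precision if tau predicts decline

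*SAP*

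**What the plan says.** **Allocation.** Protocol 6.3 states that "participant randomization will be stratified by the investigative site, tau burden (moderate versus high) as defined by flortaucipir PET" and by prior or current disease-modifying therapy, and that minimisation is used "to balance the treatment arms using three factors: investigative site, tau burden, and prior or current use" of such therapy. SAP 1.3 agrees on the strata ("patient randomization will be stratified by investigative site and tau burden (moderate versus high"), but its minimisation sentence names only site. Protocol Section 5 links elevated tau to a greater risk of clinical progression.

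**The four endpoints.** SAP 4.9 runs the analyses of 4.9.1 and 4.9.2 in both populations and puts only the moderate-tau ones in the graphical scheme. For CDR-SB, ADAS-Cog13, ADCS-iADL and MMSE, SAP 4.9.2 says: "The main analytical approach to secondary efficacy endpoints is NCS2 as described in Section 4.8.2.1". Section 4.8 is declared to be for the moderate-tau population. After the spline terms, the NCS2 list in 4.8.2.1 reads "NCS basis expansion term-by-treatment interaction (two terms), age at baseline, AChEI/memantine use at baseline (yes/no), and investigator site (pooled"). There is no tau term, and 4.9.2 adds none.

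**Other full-population models.** SAP 4.9.1 reuses the Section 4.8 models for iADRS "with the inclusion of the tau burden (moderate versus high) as defined by flortaucipir PET in the model as a baseline covariate". For volumetric MRI, 4.9.3.1 says: "Baseline tau PET category will also be included as a fixed effect to the model when analyzing full study population". Tau category also enters the models for tau PET (4.9.3.2), plasma biomarkers (4.11.1), time to progression (4.11.3, as a stratum), the ApoE subgroups (4.12.1) and follow-up (4.15.3).

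**General wording.** Protocol 9.4.2 has a broad statement ("Any stratification variables used for randomization such as investigator site and prior or current use" of disease-modifying therapy), and SAP 4.8.1 has a similar one. Both describe the disease progression model (DPM), not NCS2.

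**The concern.** A programmer who follows 4.9.2 and 4.8.2.1 literally will fit the full-population models for four secondary endpoints without a factor used to stratify randomisation. The SAP version history explains why the disease-modifying-therapy covariate was dropped, but gives no reason for leaving out tau.

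If high-tau participants decline faster, the difference between strata stays in the residual. The treatment estimate is then less precise than it need be. If the arms were in fact balanced on tau, the model standard error also exceeds the real sampling error, so the intervals are conservative and the nominal 5% test rejects less than 5% of the time under the null. These are stated secondary objectives, and readers will judge the full-population effect from these ungated estimates and intervals.

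**Working it through.** **No plan figure to reproduce.** The sample-size sections give 330 participants and a false-positive rate of about 2.4% for the DPM criterion. The power is blacked out, and none is stated for these four endpoints.

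**Inputs.** From the documents: two-sided alpha 0.05 and 1:1:1 allocation. Not in the documents, so assumed: the high-tau share p (capped at an undisclosed proportion), taken as 10-40%; and d, the difference in mean change between tau strata in within-stratum SDs, taken as 0.2-1.0.

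**Step 1: analytic size, with arms balanced on tau.** The unadjusted residual variance is 1 + p(1-p)d² times the within-stratum variance. Therefore:

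- SE ratio r = sqrt(1 + p(1-p)d²)
- true two-sided type I error = 2(1 - Φ(1.96r))
- power without tau, where the model with tau has 80% = Φ(1.96 + 0.8416 - 1.96r)

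| p | d | p(1-p)d² | r | Type I error | Power |
|---|---|---|---|---|---|
| 10% | 0.2 | 0.0036 | 1.002 | 5.0% | 79.9% |
| 20% | 0.2 | 0.0064 | 1.003 | 4.9% | 79.8% |
| 30% | 0.4 | 0.0336 | 1.017 | 4.6% | 79.1% |
| 30% | 0.8 | 0.1344 | 1.065 | 3.7% | 76.2% |
| 40% | 0.8 | 0.1536 | 1.074 | 3.5% | 75.7% |
| 30% | 1.0 | 0.2100 | 1.100 | 3.1% | 74.1% |
| 40% | 1.0 | 0.2400 | 1.114 | 2.9% | 73.2% |

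**Step 2: arms not balanced on tau.** The unadjusted standard error is then valid and the test keeps its 5% level, but the estimate is still r times less precise. Power is Φ(2.8016/r - 1.96). At p = 30% and d = 0.8 this is Φ(2.8016/1.065 - 1.96) = Φ(0.67) = 74.9%.

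**Step 3: which tau terms recover the loss.** NCS2 models the score itself with a common baseline, so a tau main effect moves only the level. A faster decline is captured only by tau-by-spline terms. This was checked by simulation with 110 per arm, exact tau balance, complete data, visits to Week 88, unstructured covariance, the Week 64/76/88 average as contrast, and 300 datasets per scenario. Slope differences are in SDs of single-visit change at Week 76, with p = 30-40%. Model SE relative to the model with tau plus tau-by-spline terms:

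| Effect of tau | No tau term | Tau main effect only |
|---|---|---|
| Baseline level only | 1.002 | 1.001 |
| Slope difference 0.4 SD | 1.02-1.03 | 1.02-1.025 |
| Slope difference 0.8 SD | 1.08-1.10 | 1.08-1.09 |

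The ratios at 0.8 SD exceed the analytic 1.065-1.074 because averaging three visits reduces noise, so the same slope difference is larger in SD units. With 300 datasets, the Monte Carlo error of a 5% rejection rate is sqrt(0.05 × 0.95/300) = 1.3 points. The simulated rejection rates are therefore too coarse to confirm the type I column of Step 1.

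**The case against.** The strongest reply is that bringing 4.9.2 into line with 4.9.1, the evident inconsistency, gains almost nothing in NCS2, because 4.9.1 adds only a main effect. The gain comes from tau-by-time terms, which neither document uses for covariate adjustment. That stands, and it shapes the fix. It does not remove the gap.

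Other replies also stand in part. The omission may be a drafting slip. The same endpoints are also analysed by DPM, whose wording on stratification variables can be read to include tau. The cap on high-tau enrolment and the stratum declines are undisclosed, and Protocol Section 5 supports prognosis only qualitatively.

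A reader might infer more than the documents support:

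- *That intervals are certainly too wide.* This needs realised balance on tau. Protocol 6.3 says so, but SAP 1.3 names only site in its minimisation sentence.
- *That the result is biased or anti-conservative.* Assignment does not depend on tau in a way that distorts a linear contrast, and any error in the test is conservative.
- *That these four endpoints are the only exception.* SAP 4.11.2 (DSST and Digital Clock) names no tau term either.
- *That MMRM has the same fault.* The covariate wording in 4.8.2.2 is open-ended, and 4.9.2 makes MMRM optional.
- *That the harm is large.* A CDR-SB scenario with declines of 1.2 against 3.0 points per 76 weeks gives a model SE of 0.288 against a true 0.258 (ratio 1.116). It assumes that high-tau participants decline 2.5 times as fast, and nothing in the documents supports that.
- *That a shifting tau mix at Week 88 distorts the comparison.* It could move the reported placebo decline, but no effect on the between-arm contrast is shown.

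**Conclusion.** The point holds as a loss of precision in ungated secondary analyses. As written, the full-population NCS2 for the four endpoints omits tau burden. If tau predicts rate of decline, the standard error is larger than necessary by roughly 0.3-10%, and power falls by under 1 to about 6 points. The extreme corners of the assumed grid are 0.2% and 0.1 points, and 11% and 7 points. The loss is nil if tau does not predict change and is probably small. The over-wide intervals and below-nominal test apply only if the arms are in fact balanced on tau. The primary analysis and the graphical testing scheme are unaffected. The change is worth making because it is nearly free, not because a conclusion depends on it.

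**What to change.** In SAP 4.9.2, state that the full-population NCS2 model for CDR-SB, ADAS-Cog13, ADCS-iADL and MMSE includes tau burden (moderate versus high) and its interaction with the two spline basis terms. The contrast and arm means should be evaluated at the observed overall tau proportions. Use the same tau-by-spline terms in the full-population NCS2 of 4.9.1.

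If the optional full-population MMRM is run, include tau burden, and tau-by-visit where data allow. Reconcile the minimisation factors in SAP 1.3 with Protocol 6.3. The moderate-tau models and the testing scheme stay as they are.

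The cost is SAP wording and three parameters in NCS2. Tau-by-visit in MMRM costs about one parameter per post-baseline visit, so about seven through Week 88, where data may be sparse. No new data are needed, since tau burden is established for every participant before randomisation. If the data are already unblinded, keep the specified model and report the adjusted one as a labelled sensitivity analysis.

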4.9.2.1. Gated Secondary Efficacy Analyses

Bretz’s graphical approach will be utilized to provide strong control of the study-wise Type I error rate for the primary and secondary clinical efficacy hypotheses at alpha level of 0.05 (Bretz et al. 2009, 2011) in the moderate tau population. The statistical significance, outlined using alpha levels in a frequentist testing paradigm, will be determined based on the following multiplicity graph of hypotheses regarding the LY3372689 slowing the cognitive and/or functional decline and tau SUVR level of AD with demonstrated presence of moderate levels of tau pathology (the blue ovals represent the high dose arm and the orange ovals represent the low dose arm):

The Bayesian DPM will be used to analyze the primary endpoint of iADRS, the NCS2 model will be utilized for secondary clinical efficacy endpoints including CDR-SB, iADL, ADAS-Cog13, and MMRM will be used to analyze the tau imaging biomarker endpoint AD-signature VOI using CereCrus as the reference region for brain tau deposition as measured by flortaucipir F18 PET standard uptake value ratio (SUVR) value.

The frequentist analyses for the clinical endpoints will utilize the endpoint averaging across Week 64, Week 76, and Week 88. The tau imaging biomarker endpoint will be analyzed based on the LS mean change from the baseline at Week 76.

As mentioned in Section 2, additional CSFs for iADRS using Bayesian DPM will be established to control the Type I error at two-sided 0.05 level in the graphical testing scheme (Section 4.9.2.1). To test the hypothesis of a disease progression benefit as measured by iADRS using the Bayesian DPM, the posterior probability of superiority in cognitive/functional slowing for each active treatment arm will be calculated. The superiority is defined by $\Pr(\text{DPR} < 0.75) > X$, where the value of X is determined via simulation to control the test at the corresponding alpha level. If the posterior probability is above the threshold for at least one active treatment arm (which controls the overall false positive rate at approximately 2.5% one-sided), then a statistical significance claim of cognitive/functional slowing will be made. Success will be declared at a graphical node if the posterior probability of at least 25% slowing of disease progression as measured by the iADRS in high dose and the low dose is greater than a certain threshold:

- Probability (at least 25 % slowing of disease progression on iADRS in LY3372689 high dose relative to placebo) > probability threshold 1.
- Probability (at least 25 % slowing of disease progression on iADRS LY3372689 low dose relative to placebo) > probability threshold 2.

These two thresholds will be calculated after unblinding at PODBL to establish the accurate probability thresholds that correspond to each alpha level as shown in graphical testing scheme above. As the thresholds can be sensitive to the underlying assumptions of placebo trajectory and the variance-covariance matrix, the methodological approach to find the probability thresholds is pre-specified below. The established thresholds will be documented in the CSR.

1. The NCS2 results for the iADRS (Section 4.8.2.1) from the moderate tau population will provide the underlying assumptions that are needed for this simulation. The following will be utilized: the LS mean placebo trajectory and the number of participants with data from the placebo arm at each visit; the pooled variance covariance matrix as estimated from the NCS2.
2. To create a null distribution, simulate multivariate normal data for the number of participants from the moderate tau population representing the placebo arm, assuming all participants have the same decline as the placebo arm from the NCS model and the same variability. The amount of data simulated for each treatment arm will reflect the exact number of participants at each visit from the placebo arm.
3. The posterior probability of at least 25% slowing is calculated by fitting the Bayesian DPM to each 100,000 simulated dataset. The Bayesian DPM as described in Section 4.8.1 but without covariate adjustment. The threshold is the lowest value at which at least $(\alpha/2 \times 100)\%$ of the simulated posterior probabilities are larger. Note that the probability threshold 2 will be re-calculated if it makes all the way down to tau imaging biomarker in the high dose arm.

The tests for the rest of the graph: CDR-SB, iADL, and ADAS-Cog13 will be based on the p-value of the difference of averaged LSM change across Week 64 to Week 88 between the treatment arms; tau imaging biomarker endpoint AD-signature VOI will be based on the p-value of the difference of LSM change at Week 76 between the treatment arms.

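### Setting the iADRS graph thresholds at the trial's own estimated placebo decline lets the cut-off fall when the test statistic rises: a nominal one-sided 2.5% runs at about 4%

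*SAP*

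**What the plan says.** SAP Section 4.9.2.1 declares success at an iADRS node when Pr(DPR < 0.75) exceeds X, where X "is determined via simulation to control the test at the corresponding alpha level". The rule of at least one active arm passing is described as one "which controls the overall false positive rate at approximately 2.5% one-sided". Section 2.1 claims strong control at 0.05 through the same graph. The null hypothesis in Section 4.8.1 is DPR = 1.

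On timing: "These two thresholds will be calculated after unblinding at PODBL".

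The inputs come from the NCS2 fit in the moderate-tau population:
- the trajectory and counts are "the LS mean placebo trajectory and the number of participants with data from the placebo arm at each visit";
- the variance is "the pooled variance covariance matrix as estimated from the NCS2", so this input alone uses all arms;
- null data are simulated "assuming all participants have the same decline as the placebo arm from the NCS model";
- on sample size, "The amount of data simulated for each treatment arm will reflect the exact number of participants at each visit from the placebo arm".

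The SAP itself says, here and in the version 4 entry of its history table, that the thresholds are sensitive to the assumed placebo trajectory. It makes no allowance for that trajectory being an estimate from the same trial.

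**The concern.** The statistic is centred on a ratio of 0.75 while the null value is 1. Its null distribution therefore depends on how far placebo declines: the larger the true decline relative to its standard error, the less often a null arm reaches a high Pr(DPR < 0.75). A cut-off set by simulation is right only for the decline used in that simulation.

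The plan uses the observed placebo decline, which is also the comparator in the DPR. If placebo happens to decline steeply, the active arm looks better and the simulated cut-off drops. If placebo happens to decline slowly, both move the other way. The two effects add, and the net result is more false positives than stated. More simulation runs do not help, because the error lies in the input.

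At stake are the statistical-significance claim for iADRS and entry to the gated secondary tests.

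**Working it through.** **Inputs from the SAP.** Statistic Pr(DPR < 0.75) > X; null DPR = 1; trajectory and counts from placebo; pooled covariance; overall one-sided 2.5%.

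**Assumptions.** The design decline and SD are redacted in SAP Section 5, the moderate-tau sample size is not given, and the node alphas are in a figure not shown. For a closed form, let p and a be the estimated placebo and active declines, each normal with true mean D (under the null) and standard error s, with a flat prior.

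**1. Reproduce the stated level with D known.** Pr(DPR < 0.75) = Φ((0.75p − a)/(1.25s)), since √(1 + 0.75²) = 1.25. Under the null the argument has mean −0.25D/(1.25s) = −0.2D/s and SD 1. The 2.5% cut-off on this scale is 1.96 − 0.2D/s. Used with the true D, it gives exactly 2.5% per arm. For at least one arm, with alpha split 1.25%/1.25% (correlation 0.5625/1.5625 = 0.36), the rate is 2.4%. The claim therefore holds if D is known.

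**2. Put the placebo estimate in place of D, as planned.** Reject when (0.75p − a)/(1.25s) > 1.96 − 0.2p/s. Multiplying by 1.25s gives 0.75p − a > 2.45s − 0.25p, that is, p − a > 2.45s. The null SD of p − a is √2·s = 1.414s, so z = 2.45/1.414 = 1.732 and the level is **4.16%**. D and s cancel, so the redacted values do not matter for this result.

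The factor 1.25/1.414 = 0.884 applies at any node level:

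| Nominal one-sided | z | 0.884z | Actual |
|---|---|---|---|
| 2.5% | 1.960 | 1.732 | 4.16% |
| 2.0% | 2.054 | 1.815 | 3.5% |
| 1.25% | 2.241 | 1.981 | 2.38% |
| 0.5% | 2.576 | 2.277 | 1.1% |

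At least one arm (correlation now 0.5): 4.3% for either a 1.25%/1.25% or a 2.0%/0.5% split.

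**3. Simulate the planned model.** Three arms, weeks 0-88, random intercept and the SAP priors, with N(0, 0.25) on log(DPR) read both as variance and as precision. The threshold was recalculated from each trial's NCS2 placebo trajectory, with 32,000 null trials per scenario. Variances were plugged in and covariates omitted. Assumed ranges: 60-100 moderate-tau participants per arm, a 76-week decline of 8-16 points, SD of change about 13.

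| Cut-off set at | Per arm, nominal 2.5% | At least one arm |
|---|---|---|
| True decline | 2.3-2.5% | 2.1-2.5% |
| Placebo estimate (the plan) | 3.8-4.2% | 4.0-4.4% |
| Estimate pooled over three arms | 2.3-2.5% | 2.1-2.4% |

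**4. Visit counts, a separate issue.** Let the active arm carry a fraction f of the placebo arm's information while the cut-off is still set from placebo counts. With k = √(0.5625 + 1/f) and c = 0.75 + 0.2k, rejection is c·p − a > 1.96k·s. Hence z = (1.96k − (c − 1)D/s)/√(c² + 1/f). This does depend on D/s, for which 6, 8.6 and 11 are assumed:

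| f | D/s = 6 | D/s = 8.6 | D/s = 11 |
|---|---|---|---|
| 0.8 | 4.8% | 5.1% | 5.4% |
| 0.9 | 4.4% | 4.6% | 4.7% |
| 1.0 | 4.2% | 4.2% | 4.2% |
| 1.1 | 3.9% | 3.8% | 3.7% |
| 1.25 | 3.6% | 3.4% | 3.2% |

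**5. Check the repairs.** With the pooled trajectory m = (p + a + a₂)/3, where a₂ is the other active arm, rejection is 0.75p − a + 0.25m > 2.45s. The left side is 0.833p − 0.917a + 0.083a₂, with variance (0.694 + 0.840 + 0.007)s² = 1.542s². So z = 2.45/1.242 = 1.973 and the level is 2.42%. With Pr(DPR < 1), the statistic is (p − a)/(1.414s), whose null distribution is free of D, so the level is 2.5%.

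**The case against.** The strongest reply is about scope. Whether the trial met its primary endpoint is decided in SAP Section 2 by a fixed rule, Pr(at least 25% slowing) > 0.6, which this calibration does not touch. Thresholds 1 and 2 are additional criteria for the graph in a Phase 2 study, and the SAP says only that the overall rate is approximately 2.5%. All of that stands. A reader might infer that the primary success decision is compromised; the documents do not support that reading. The claim that is affected is statistical significance on iADRS, and 4.0-4.4% is too far from 2.5% to be covered by the word approximately.

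A reader might also infer that the visit counts make the cut-off follow the result. They do not. Counts are unrelated to chance variation in the decline, and the mismatch lowers the error when active arms carry more data. Nothing in the documents says active arms will lose more; SAP Section 5 expects about 80 completers in each arm.

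A third tempting reading is an error of 5% or more. That needs active arms with roughly 20% less information than placebo, which is an assumption. With equal data the figure is about 4%.

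The sponsor may add that the recipe was fixed before unblinding. That removes discretion but not the dependence between cut-off and statistic.

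**Conclusion.** The calibration does not deliver the level that the SAP states for the iADRS nodes. With equal data per arm, a nominal 2.5% runs at about 4.2% in closed form (3.8-4.2% simulated), 1.25% runs at about 2.4%, and the overall one-sided rate is about 4.0-4.4%. That is up to about 1.7 times the stated rate (4.3/2.5). The direction is anti-conservative.

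The closed-form figure rests on normality, a flat prior and equal counts, and not on any redacted design value. The simulated figures rest on the assumed decline, SD and sample size. Because the node alphas are not visible, an individual node may start below 2.5%; the overall rate is inflated under both alpha splits tried. The use of placebo counts is a second, smaller fault of unknown sign: about 5% at f = 0.8 and about 3.4% at f = 1.25, taking D/s = 8.6.

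**What to change.** Change steps 1-3 of SAP Section 4.9.2.1 in one of two ways.

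(a) Take the null trajectory from the NCS2 estimate pooled over all three arms, as the covariance already is. The statistic and the rest of the recipe stay, and the level returns to about 2.3-2.5%. This holds when all arms decline alike. An effective dose makes the pooled decline shallower and raises the cut-off (conservative for the other dose); a harmful dose does the opposite.

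(b) Test the nodes with Pr(DPR < 1) > X, with X from the same simulation, and keep the 25% margin as a separate clinical-relevance criterion. In the closed form this removes the dependence on the placebo decline altogether.

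In either case, simulate each arm with its own observed number of participants at each visit.

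The cost is SAP wording and simulation code; neither option needs a nested simulation. The cut-off becomes somewhat stricter, so apparent power falls. The part lost is the part that the excess error had supplied.
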